#### 1.2 Data cleaning and verification

All data will be cleaned and verified prior to statistical analysis. The study site will be visited by the Monitor periodically at times agreed on with the Investigator. At the time of each monitoring visit, the Monitor will review the completed CRFs to ascertain that all items have been completed and that the data provided are accurate and obtained in the manner specified in the protocol. The Monitor will also check that the data in the CRF are consistent with the clinical records (Source Data Verification [SDV]) and that study results are recorded completely and correctly. The data manager will ensure that clean data is submitted to the statistician for analysis. The statistician will cross-check that the available data for analysis is clean. Any data cleaning queries will need to be resolved before statistical analyses.

#### 1.3 Locking the dataset

After data cleaning and responding to all data queries, the clean data will be locked normally in the database that was used for data capturing. The data may also be locked and stored in other user-friendly formats such as MS Excel and Stata. The locked data will be stored at an identifiable secure place and should be available to the relevant researchers upon request following proper request procedures.

---

## STATISTICAL ANALYSIS PLAN

### 1.4 Data format and Analysis logs

Prior to dispensing data to the trial statistician, the head of data management will make sure that the data to be sent to the trial statistician is clean. This will help the statistician to provide the analysis results in a timely manner as there will be a reduced amount of queries if clean data is provided to the trial statistician. Data will be given to the Trial Statistician by the head of Data Management (or designated person) in a format that is compatible with statistical software reading. Statistical analyses will be performed in Stata, version 17 or higher or R software. Statistical programs and output logs will be kept for all analysis and made available upon request.

### 1.5 Interim analyses

We plan to have 2 interim analyses on clinical, laboratory and electrocardiographic data to assess the safety of the novel TACTs. The interim reports will be reviewed by DSMB. The interim analyses will be performed after the first 100 patients, first 500 patients and at additional time-points before the planned interim analyses, as indicated by the DSMB after their review, if deemed necessary. After this, safety analysis will be performed based on recommendations by the DSMB. No stopping rules both statistical as well as clinical will be specified. The need to stop the trial will be based on the perception of the accumulating data by the DSMB. The main strategy of analysis will focus on safety data although efficacy data may also be presented.

The Trial coordinator in collaboration with the Trial Statistician will produce the report for the DSMB. Only relevant data included in a specific interim report will be made available to the DSMB members at the time of sending the report. During a DSMB meeting, the report will be presented to the members by the study coordinator in line with the meeting agenda. For a normally scheduled DSMB meeting, the report will be sent out to the members at least a week before the meeting.

---

## 2. Introduction

This is a multicentre study in 8 different countries in Africa. The study was designed in a way that each centre has 80% power to detect a difference in the efficacy outcomes, if they exist.

Artemisinin combination therapies (ACTs) have been a major contributor to the substantial reductions in global malaria morbidity and mortality over the last decade. However, further gains are threatened by the recent emergence of artemisinin and partner drug resistance in Southeast Asia, a region which has been the epicentre for the evolution and spread of resistance to every important class of antimalarials. Loss of efficacy of first line ACTs jeopardizes current malaria control and elimination efforts and will accelerate the spread of drug resistance. A major concern is that artemisinin and partner drug resistance may spread across a wider geographic area, as chloroquine resistance did in the 1960s and 1970s, moving from Southeast Asia to the Indian subcontinent and subsequently to Africa, which bears the vast majority of the global malaria burden. Furthermore, artemisinin resistance could worsen by extending beyond the current ring stage parasite resistance, although this has until now not been observed. We aim to assess the extent of the spread or the *de novo* emergence of resistance to the antimalarials in the combinations through detailed *in vivo* and *in vitro* assessments and to study the pharmacokinetics and inter-drug interactions of the drugs, the parasite- and host-related factors affecting treatment outcomes. Finally, we aim to gain insights into the spread of resistance mediated by population movements and parasite gene flows in general through travel surveys and geographic localization of parasite genetic data.

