15. STATISTICAL CONSIDERATIONS

15.1. Sample size justification

These studies will have a non-inferiority trial design. Each site will be powered for the efficacy endpoint. For the safety and tolerability endpoint, the sample size will be pooled across the study

sites to achieve the desired power of at least 80% to detect rare events.

For sample size calculations, the following assumptions have been used: The expected efficacy of ACTs (AL, ASMQ) in these countries is expected to be approximately 96%. The matching TACT efficacy is assumed to be at least 90% under the null hypothesis of inferiority based on the WHO 90% efficacy threshold. However preliminary TRACII study data suggest that TACTs potentially may have a better efficacy of 1% to 2% higher in favour of TACT (i.e. a conservative 97%-98% efficacy or higher).

A one-sided alpha of 0.025 has been used in sample size calculations as non-inferiority is in one direction. For the efficacy outcome, a sample size of 60 subjects in the ACT plus placebo arms and 120 subjects in the matching TACT would be needed to achieve approximately 80% power to detect a non-inferiority margin difference between the group efficacy of -6%. With an additional 20% to cover for loss to follow up, we would therefore need 72 subjects in ACT plus placebo group and 144 subjects in the matching TACT in each of the sites. Since there will be 4 arms, it means we will need 432 subjects per site with 144 subjects in the two ACT arms combined and 288 subjects in the two TACT arms combined.

The sample sizes are in the ratio of 1:2 for ACT vs TACT to allow us to collect more safety and tolerability data for TACTs, which could be beneficial to both policy makers as well as future malaria patients [26, 27]. With these numbers of recruited subjects in Africa, we will have a power above 80% to detect an increase of the incidence of adverse events from 1 in 100 to 3 in 100 for subjects treated with ACT as compared to the matching TACT, respectively.

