15.2.1. Proportions

These will be compared using chi squared or Fisher's exact test, as appropriate. Crude proportions will be calculated with the exact 95% confidence intervals (CI), where relevant.

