### 2.2.1 Determination of sample size

These studies will have a non-inferiority trial design. Each site will be powered for the efficacy endpoint. For the safety and tolerability endpoint, the sample size will be pooled across the study sites to achieve the desired power of at least 80% to detect rare events.

For sample size calculations, the following assumptions have been used: The expected efficacy of ACTs (AL, ASMQ) in these countries is expected to be approximately 96%. The matching TACT efficacy is assumed to be at least 90% under the null hypothesis of inferiority based on the WHO 90% efficacy threshold. However preliminary TRACII study data suggest that TACTs potentially may have a better efficacy of 1% to 2% higher in favour of TACT (i.e. a conservative 97%-98% efficacy or higher).

A one-sided alpha of 0.025 has been used in sample size calculations as non-inferiority is in one direction. For the efficacy outcome, a sample size of 60 subjects in the ACT plus placebo arms and 120 subjects in the matching TACT would be needed to achieve approximately 80% power to

---

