**Table 2a Comparison of Day 42 PCR corrected Efficacy as proportions of Various ACTs with matching TACTs by sites**

## STATISTICAL ANALYSIS PLAN

Site	PCR corrected ACPR at day 42, n/N, (%)				Risk difference (95% CI, p-value)	
	AL+Placebo (N=XXXX)	AL+AQ (N=XXXX)	ASMQ+Placebo (N=XXXX)	ASMQ + PPQ (N=XXXX)	AL+Placebo vs AL+AQ	ASMQ+Placebo vs ASMQ+PPQ
Burkina Faso	XX/XXX (XX.X)	XX/XXX (XX.X)	XX/XXX (XX.X)	XX/XXX (XX.X)	XX.X (XX.X - XX.X, 0.XXX)	XX.X (XX.X - XX.X, 0.XXX)
DR Congo	XX/XXX (XX.X)	XX/XXX (XX.X)	XX/XXX (XX.X)	XX/XXX (XX.X)	XX.X (XX.X - XX.X, 0.XXX)	XX.X (XX.X - XX.X, 0.XXX)
Gambia	XX/XXX (XX.X)	XX/XXX (XX.X)	XX/XXX (XX.X)	XX/XXX (XX.X)	XX.X (XX.X - XX.X, 0.XXX)	XX.X (XX.X - XX.X, 0.XXX)
Guinea	XX/XXX (XX.X)	XX/XXX (XX.X)	XX/XXX (XX.X)	XX/XXX (XX.X)	XX.X (XX.X - XX.X, 0.XXX)	XX.X (XX.X - XX.X, 0.XXX)
Niger	XX/XXX (XX.X)	XX/XXX (XX.X)	XX/XXX (XX.X)	XX/XXX (XX.X)	XX.X (XX.X - XX.X, 0.XXX)	XX.X (XX.X - XX.X, 0.XXX)
Nigeria	XX/XXX (XX.X)	XX/XXX (XX.X)	XX/XXX (XX.X)	XX/XXX (XX.X)	XX.X (XX.X - XX.X, 0.XXX)	XX.X (XX.X - XX.X, 0.XXX)
Tanzania	XX/XXX (XX.X)	XX/XXX (XX.X)	XX/XXX (XX.X)	XX/XXX (XX.X)	XX.X (XX.X - XX.X, 0.XXX)	XX.X (XX.X - XX.X, 0.XXX)
Rwanda	XX/XXX (XX.X)	XX/XXX (XX.X)	XX/XXX (XX.X)	XX/XXX (XX.X)	XX.X (XX.X - XX.X, 0.XXX)	XX.X (XX.X - XX.X, 0.XXX)
All sites	XX/XXX (XX.X)	XX/XXX (XX.X)	XX/XXX (XX.X)	XX/XXX (XX.X)	XX.X (XX.X - XX.X, 0.XXX)	XX.X (XX.X - XX.X, 0.XXX)

[figure not shown]
[figure not shown]

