## STATISTICAL ANALYSIS PLAN

**Figure 3 The difference between TACT vs ACT of Day 42 PCR corrected Efficacy as proportions by site****Table 2b Comparison of Day 42 PCR corrected Efficacy using survival methods of Various ACTs with matching TACTs by sites**

Site	PCR corrected ACPR at day 42, Cumulative recurrent infection free percentage (efficacy), % (95% CI)				Hazard ratio (95% CI, p-value)	
	AL+Placebo (N=XXXX)	AL+AQ (N=XXXX)	ASMQ+Placebo (N=XXXX)	ASMQ + PPQ (N=XXXX)	AL+Placebo vs AL+AQ	ASMQ+Placebo vs ASMQ+PPQ
Burkina Faso	XX.X (XX.X - XX.X)	XX.X (XX.X - XX.X)	XX.X (XX.X - XX.X)	XX.X (XX.X - XX.X)	XX.X (XX.X - XX.X, 0.XXX)	XX.X (XX.X - XX.X, 0.XXX)
DR Congo	XX.X (XX.X - XX.X)	XX.X (XX.X - XX.X)	XX.X (XX.X - XX.X)	XX.X (XX.X - XX.X)	XX.X (XX.X - XX.X, 0.XXX)	XX.X (XX.X - XX.X, 0.XXX)
Gambia	XX.X (XX.X - XX.X)	XX.X (XX.X - XX.X)	XX.X (XX.X - XX.X)	XX.X (XX.X - XX.X)	XX.X (XX.X - XX.X, 0.XXX)	XX.X (XX.X - XX.X, 0.XXX)
Guinea	XX.X (XX.X - XX.X)	XX.X (XX.X - XX.X)	XX.X (XX.X - XX.X)	XX.X (XX.X - XX.X)	XX.X (XX.X - XX.X, 0.XXX)	XX.X (XX.X - XX.X, 0.XXX)
Niger	XX.X (XX.X - XX.X)	XX.X (XX.X - XX.X)	XX.X (XX.X - XX.X)	XX.X (XX.X - XX.X)	XX.X (XX.X - XX.X, 0.XXX)	XX.X (XX.X - XX.X, 0.XXX)
Nigeria	XX.X (XX.X - XX.X)	XX.X (XX.X - XX.X)	XX.X (XX.X - XX.X)	XX.X (XX.X - XX.X)	XX.X (XX.X - XX.X, 0.XXX)	XX.X (XX.X - XX.X, 0.XXX)
Tanzania	XX.X (XX.X - XX.X)	XX.X (XX.X - XX.X)	XX.X (XX.X - XX.X)	XX.X (XX.X - XX.X)	XX.X (XX.X - XX.X, 0.XXX)	XX.X (XX.X - XX.X, 0.XXX)
Rwanda	XX.X (XX.X - XX.X)	XX.X (XX.X - XX.X)	XX.X (XX.X - XX.X)	XX.X (XX.X - XX.X)	XX.X (XX.X - XX.X, 0.XXX)	XX.X (XX.X - XX.X, 0.XXX)
All sites	XX.X (XX.X - XX.X)	XX.X (XX.X - XX.X)	XX.X (XX.X - XX.X)	XX.X (XX.X - XX.X)	XX.X (XX.X - XX.X, 0.XXX)	XX.X (XX.X - XX.X, 0.XXX)

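### The SAP introduction claims 80% power per centre to detect an efficacy difference; the sites are sized for non-inferiority, and power to detect a difference is about 11-14% at the plan's own rates

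*SAP*

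**What the plan says.** The SAP introduction (section 2) tells the reader: "The study was designed in a way that each centre has 80% power to detect a difference in the efficacy outcomes, if they exist".

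The sample-size text, which is the same in SAP 2.2.1 and protocol 15.1, gives a different purpose: "These studies will have a non-inferiority trial design. Each site will be powered for the efficacy endpoint". It adds: "A one-sided alpha of 0.025 has been used in sample size calculations as non-inferiority is in one direction". The size follows in protocol 15.1: with 60 ACT subjects, "120 subjects in the matching TACT would be needed to achieve approximately 80% power to detect a non-inferiority margin difference" of -6 points. On the control rate it says "The expected efficacy of ACTs (AL, ASMQ) in these countries is expected to be approximately 96" per cent. TACT is placed at 90% under the null of inferiority, and 97% to 98% or higher is mentioned as a possible true value.

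For reporting, SAP Table 2a has a column headed "Risk difference (95% CI, p-value") for each matched pair at each site, and its null hypothesis is not stated. The sub-columns name the ACT first. The caption of SAP Figure 3 names the TACT first: "The difference between TACT vs ACT of Day 42 PCR corrected Efficacy as proportions by site". Protocol 15.2.1 says of proportions in general: "These will be compared using chi squared or" Fisher's exact test. SAP 3.3 says non-inferiority will be judged from a confidence interval.

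**The concern.** Power to show non-inferiority and power to detect a difference answer different questions. In the first, the null is a deficit of 6 points or more, and the distance that drives power is the true difference plus 6. In the second, the null is equality and only the true difference counts. A design can have 80% of one and very little of the other. The introduction attaches the figure for the first to the second.

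This matters because the primary objective is a comparison within each site, so the site rows of Table 2a are the primary results. A reader who has been told that each site had 80% power to find a difference will give weight to a p-value above 0.05 beside a site's risk difference. If that p-value tests equality, it says little at these sizes. Because neither its null nor the direction of subtraction is stated, the table does not prevent that mistake.

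The 80% non-inferiority figure also depends on an assumption that the plan leaves as a range.

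**Working it through.** **Inputs** (SAP 2.2.1, protocol 15.1): pA = 0.96; pT = 0.97 to 0.98 as the possible truth and 0.90 under the null; margin 0.06; one-sided alpha 0.025; allocation 1:2; 60 and 120 evaluable (72 and 144 enrolled).

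**Step 1. Reproduce the plan's sample size.** With unpooled variance,

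nA = (1.960 + 0.842)² × [pA(1−pA) + pT(1−pT)/2] / (pT − pA + 0.06)²

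At pT = 0.98 this is 7.849 × (0.0384 + 0.0098) / 0.08² = 59.1, so 60 ACT and 120 TACT. This matches the plan. At pT = 0.97 the formula needs 85 ACT subjects, and at 0.96 it needs 126.

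**Step 2. Non-inferiority power at 60/120.** Power = Φ[(pT − pA + 0.06)/SE − 1.96], where SE² = pA(1−pA)/60 + pT(1−pT)/120. The last column enumerates all binomial outcomes and counts those whose Wald lower bound exceeds -6 points.

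| True TACT | SE | Normal formula | Exact enumeration of Wald bound |
|---|---|---|---|
| 98% | 0.02834 | Φ(0.863) = 80.6% | 90% |
| 97% | 0.02971 | Φ(0.396) = 65.4% | 73% |
| 96% | 0.03098 | Φ(−0.023) = 49.1% | 54% |

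The normal formula reproduces the plan's 60/120 and its approximately 80%, and it does so at 98%.

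**Step 3. Power to detect a difference.** This is a two-sided 5% test of equality with ACT at 96%, by exact binomial enumeration of the rejection regions:

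| Evaluable | True TACT | Fisher | Chi-squared |
|---|---|---|---|
| 60/120 | 98% | 11.3% | 14.2% |
| 60/120 | 97% | 5.4% | 6.7% |
| 60/120 | 90% | 20.8% | 26.8% |
| 72/144 | 98% | 13.1% | 15.4% |
| 72/144 | 90% | 27.1% | 32.3% |

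The pooled normal formula can be checked by hand for 96% against 98% at 60/120. The pooled rate is (57.6 + 117.6)/180 = 0.9733, so SE0 = √(0.9733 × 0.0267 × 0.025) = 0.02547. Power = Φ[(0.02 − 1.96 × 0.02547)/0.02834] = Φ(−1.056) = 14.6%.

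**Step 4. What 80% would require.** By the pooled normal formula, 80% power to detect 96% against 98% at 1:2 needs about 817 ACT and 1,634 TACT subjects per site. With 60/120 and ACT at 96%, TACT would have to fall to between 81% (83.4% power) and 82% (78.9%).

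**Step 5. Consequence for an equality p-value.** If TACT were truly at 90% and ACT at 96%, p would exceed 0.05 with probability 1 − 0.268 = 73% (chi-squared) to 1 − 0.208 = 79% (Fisher) at 60/120, and 68% to 73% at 72/144.

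**The case against.** The fair reply is that this is one careless sentence in an introduction. The SAP calls the trial a non-inferiority trial, 2.2.1 attaches the power to the -6 point margin, and 3.3 bases the conclusion on a confidence interval. The sample size reproduces. All of that stands: the fault is a contradiction in wording, and it changes neither the design nor the decision rule.

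Three stronger readings are tempting, and the documents do not support them.

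- *That Table 2a's p-values are equality tests.* The SAP does not say. The chi-squared and Fisher tests come from protocol 15.2.1, part of a brief overview not tied to the primary comparison. The supportable statement is that the null is undefined.
- *That the sponsor intends to read a non-significant p-value as no difference.* No section proposes this. It is a risk of misreading, which the introductory sentence increases.
- *That Table 2a and Figure 3 contradict each other on direction.* Table 2a's sub-columns name a pair without giving a subtraction order. The sign is unspecified; it has not been shown to be reversed.

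Nor is the TACT assumption absent, since a range of 97% to 98% is printed. What is missing is which value gave 80%. Finally, the normal and exact non-inferiority figures differ by 5 to 9 points, so any power written into the SAP must name its method.

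**Conclusion.** The SAP introduction states a power that the design does not have and that its own sample-size section does not claim. For one matched pair at one site with 60/120 evaluable, power to detect a difference is about 11-14% at 96% against 98%, and about 21-27% at 96% against 90%. The approximately 80% belongs to non-inferiority at -6 points and holds, by the formula that reproduces the plan's numbers, only if TACT efficacy is about 98%. At 97% the same formula gives 65%, and at equality 49%; exact enumeration gives 90%, 73% and 54% for the three cases.

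These results assume ACT efficacy of 96%, one-sided 0.025 for non-inferiority and two-sided 5% for equality. They do not describe the all-sites row. With 480/960 evaluable in the AL pair, the pooled normal formula gives about 59% for 96% against 98%, which is higher but still under 80%.

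The point deserves correction because the within-site comparison is the primary objective. It does not put the sample size in doubt.

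**What to change.** 1. Replace the sentence in SAP section 2 with text to this effect: *Each site has about 80% power to show non-inferiority (margin -6 points, one-sided alpha 0.025, 60 ACT and 120 TACT evaluable) if ACT efficacy is 96% and TACT efficacy 98%. By the same unpooled normal formula the power is about 65% if TACT is 97% and 49% if the two are equal; exact enumeration of the Wald bound gives 90%, 73% and 54%. Sites are not powered to detect a difference.*
2. In SAP 2.2.1 and protocol 15.1, state which TACT efficacy and which method produced the 80%.
3. In Table 2a and Figure 3, define the difference as TACT minus ACT.
4. In Table 2a, state the null of the p-value and report the one-sided p-value for TACT minus ACT at or below -6 points. If an equality p-value is kept, label it as such and as secondary.

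The cost is some SAP and protocol wording and one table column, and the stated power will read less favourably. No data collection, sample size or confidence-interval rule changes.

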## STATISTICAL ANALYSIS PLAN

The principle that multiple drugs with independent mechanisms of action prevent the emergence of drug resistance is proven in a range of human diseases. In HIV and tuberculosis for example, the occurrence and spread of drug resistance can be prevented by use of a combination of three or more antiretroviral or antimycobacterial therapies respectively, but until now this was not thought necessary in malaria. In malaria there is a fortuitous inverse correlation between susceptibility to artemether-lumefantrine and amodiaquine or artesunate-mefloquine and piperaquine which will be exploited in the TACTs.

### 2.1. Study objectives and endpoints

#### 2.1.1. Primary objective

To compare the efficacy of the ACTs and TACTs as defined by the 42-day PCR corrected adequate clinical and parasitological response (ACPR) within each individual site.

Matching comparisons of ACT and TACT are as follows:

- AL+Placebo versus AL+AQ
- ASMQ+ Placebo versus ASMQ+PPQ

#### 2.1.2. Primary endpoint

42-day efficacy defined as PCR-corrected adequate clinical and parasitological response (ACPR).

*(NB, WHO definition of ACPR: absence of parasitaemia at day 42 irrespective of axillary temperature and without previously meeting any of the WHO criteria for early or late treatment failure, or late parasitological failure.)*

#### 2.1.3. Secondary objectives and endpoints

- To compare the safety and tolerability of ACTs and TACTs within and across sites and regions, including comparisons of 'non-matching' ACTs vs TACTs (AL+Placebo versus ASMQ+PPQ, ASMQ+Placebo versus AL+AQ).
  - Incidence of adverse events and serious adverse events within the first 42 days including markers of hepatic, renal or bone marrow toxicity; cardiotoxicity, in particular QT or QTc-interval above 500 ms at timepoint H4 and H52/H64 and between these time points; change from baseline in haemoglobin at days 3, 7, 28, stratified for G6PD status/genotype; proportion of subjects requiring retreatment due to vomiting within 1 hour after administration of the study drugs; proportion of subjects that reports completing a full course of observed TACT or ACT without withdrawal of consent or exclusion from study because of drug related serious adverse event
  - Changes in the electrocardiogram (such as prolongation of the QTc-interval) in patients treated with TACT versus standard ACT
- To compare additional measures of treatment efficacy between treatment arms, including the 63-day ACPR, the post-treatment prophylactic effect of ACTs and TACTs defined as the 42-day & 63-day PCR uncorrected ACPR, gametocyte carriage, parasite clearance rates and fever clearance.

## STATISTICAL ANALYSIS PLAN

- Comparing 63-day PCR corrected and uncorrected efficacy; 42-day PCR uncorrected efficacy between ACT and TACT
- Parasite clearance half-life assessed by microscopy as primary parameter to determine parasite clearance; proportion of subjects with microscopically detectable *P. falciparum* parasitaemia at Day 3; fever clearance time (i.e. the time taken for the tympanic temperature to fall below 37.5 °C in patients who were febrile at inclusion); proportion of subjects with gametocytaemia during and after treatment stratified by presence of gametocytes at enrolment.
- To assess pharmacokinetic and pharmacodynamic interactions between antimalarials in ACT and TACTs
  - Pharmacokinetic profiles and interactions (including Cmax and AUC) of artemisinin-derivatives and partner drugs in ACT and TACT treated subjects in correlation with pharmacodynamics measures of drug efficacy; day 7 plasma levels of partner drugs in correlation with treatment efficacy and treatment arm

### 2.1.4. Exploratory objectives and endpoints

- To compare measures of treatment efficacy between treatment arms
  - Comparison of 63-day vs 42-day PCR corrected and uncorrected efficacy of ACTs vs TACTs
- To assess molecular genetic and transcriptomic correlates for artemisinin and partner drug resistance of the infecting *P. falciparum* strains
  - Whole genome sequence and transcriptome analysis of artemisinin and/or partner drug-resistant parasites compared with drug-sensitive parasites
- To compare *in vitro* susceptibility profiles of *P. falciparum* isolates across geographic regions
  - In vitro sensitivity of *P. falciparum* to artemisinins and partner drugs according to study sites and genotype
- To compare the selective effect of ACTs versus TACTs on parasites carrying mutations associated with resistance to antimalarial drugs
  - Proportions of recurrent infections with parasites carrying mutations of known functional significance
  - Proportions of specimens collected at baseline with parasites carrying mutations of known functional or operational significance (pfkelch13, pf crt, pfmdr1, pfdhfr, pfdhps, pfplasmepsin2, partial or complete deletions of pfhrp2 and other current parasite genetic markers associated with resistance or identified over the course of the study)
- To obtain additional safety data (in particular incidence, rate and magnitude of haemolysis) on the deployment of single low dose primaquine, stratified according to G6PD status/genotype
  - Change in hematocrit on day 1 to 7, 14, 21, 28, 35 and 42 according to geographical location and study arm, stratified for G6PD status
- To obtain additional data on the effect of the host genotypes known to affect pharmacokinetics and pharmacodynamics of antimalarials
  - Correlation between the host genotype (e.g., CYP2D6, CYP3A4, KCNQ1/LQT1, KCNH2/LQT2, SCN5A/LQT3) and the pharmacokinetics and pharmacodynamics of antimalarials.
- To assess new methods for determination of gametocytaemia, parasite phenotypes and genotypes
  - Novel assays to be tested

